1 SYNOPSIS

COMPOUND: Aubagio® (Teriflunomide	2)
STUDY No: TERIFL08182	
TITLE	A prospective, observational, UK study to describe patient reported quality of life in relapsing remitting multiple sclerosis patients treated with Aubagio® (teriflunomide) 14 mg in routine clinical practice.
LOCATION	United Kingdom
STUDY OBJECTIVES	Primary objectives: To describe the change in health related quality of life (HRQoL) at 2 years, in patients commencing treatment with Aubagio® in routine clinical practice for relapsing remitting multiple sclerosis (RRMS).
	Secondary objectives To describe the change in the following patient reported outcomes (PROs) at 2 years, in patients commencing on treatment with Aubagio® in routine clinical practice for RRMS: • Fatigue • Anxiety and depression • Cognition
	 Sexual dysfunction Disease progression Treatment satisfaction Treatment adherence
	To describe the number of relapses during the two year study period in patients commencing on treatment with Aubagio® in routine clinical practice for RRMS.
	To describe health economic outcomes in patients with RRMS treated with Aubagio® assessed by the number of scheduled and unscheduled healthcare provider (HCP) encounters and emergency visits, as well as productivity loss.
	Exploratory objective Additional exploratory objective will be to evaluate primary and secondary objectives in at least 4 specific subgroups: treatment naïve patients, patients previously treated with a MS disease modifying therapy (DMT) within the past 2 years, injectable switch patients and oral switch patients.
STUDY DESIGN & DURATION	Multi-centre, prospective non-interventional study.
	This is a 2 year prospective, observational UK study to describe HRQoL, PROs in RRMS patients treated with Aubagio® (teriflunomide) 14 mg in a routine clinical practice.
	The decision to treat with Aubagio® must be made prior to and independently from the proposal to enrol the patient on this study. All patients must be prescribed Aubagio® in accordance with the UK

TERIFL08182	Version number: Final 2.0			
	summary of product characteristics (SmPC).			
	Visits will be scheduled by the treating HCP according to patient specific needs and local clinical practice. For purposes of this study, 6 visits are expected: study baseline (Visit 1), with follow-up visits at months 3 (if part of routine clinical setting), 6, 12, 18 (if part of routine clinical practice) and 24.			
STUDY POPULATION	Inclusion Criteria			
	 Adult patients (>18 years old) with RRMS according to a neurologist's diagnosis, where the physician and patient have decided to start treatment with Aubagio® according to the SmPC. 			
	2. Initiated Aubagio® treatment for the first time within 4 weeks of study entry			
	Patient having signed written informed consent			
	4. Patients who are willing and able to fill out the questionnaires for the full duration of the study.			
	Note: If a designated caregiver is available to assist the patient, they may physically complete the questionnaire for the patient. A nurse or other health care professional may assist with instructing the patient on how to complete a questionnaire.			
	Exclusion criteria:			
	 Patients with contraindications to Aubagio® according to SmPC Patients who are currently participating in an investigational interventional study if, in the judgment of the Investigator, such participation would interfere with the current study. Patients who are unwilling or unable to complete any questionnaire to be used in the study Women of child bearing age who are not willing to use an effective form of contraception 			
RECRUITMENT MODALITIES	Selection of Investigator			
	Investigators who are experienced in the treatment of patients with RRMS will undergo a feasibility assessment performed by Sponsor representatives. Selection of patients			
	Consecutive recruitment after decision to begin Aubagio® therapy, and determination of patient eligibility and willingness to participate. The decision to treat with Aubagio® must be made before considering a patient's entry into the study.			

Version number: Final 2.0

FNDPOINTS

Primary Endpoint

Mean change in Multiple Sclerosis Impact Scale (MSIS-29) scores from baseline to month 24.

Secondary endpoints

Clinical outcomes:

- Number of relapses (since baseline) at each visit and at month 24 Patient reported outcomes:
 - Disability accumulation: change in Patient Determined Disease Steps (PDDS) over time at each visit (except visit 2) and at month 24 compared with baseline
 - Fatigue: change in Fatigue score, assessed using the MFIS-5, at each visit (except visit 2) and at month 24 compared with baseline
 - Anxiety and Depression: Change in anxiety and depression at each visit (except visit 2) and at month 24 compared with baseline, as measured by the Hospital Anxiety and Depression Scale (HADS)
- Cognition: Change in cognition at each visit and at month 24 compared with baseline, as measured by the Symbol Digit Modalities Test (SDMT).
- Sexual Function: Change in intimacy and sexual health at each visit and at month 24 compared with baseline as measured by MSISQ-19.
- Treatment satisfaction: change in Treatment Satisfaction Questionnaire for Medication version 1.4 (TSQM v1.4) score over time, from baseline to each visit (except visit 2) and month 24.
- In patients switching from another disease modifying treatment (DMT): change in TSQM from baseline to month 6 and to month 24
- For naïve patients: change in TSQM from month 6 to month 24.
- Treatment adherence: number of missed doses of Aubagio®

Health economics outcomes:

- Number of scheduled and unscheduled HCP encounters
- Number of emergency visits
- Change in work capacity reported using the Health Related Productivity Question-MS (HRPQ-MS) at months 12 and 24 compared with baseline.

Safety endpoint

Adverse events (AEs), serious adverse events (SAEs), and AEs of special interest (AESIs) recorded at each visit according to standard clinical practice. Patients will be followed with laboratory monitoring in a regular healthcare setting in line with local approved label requirements and the risk management plan (RMP) for Aubagio®.

MAIN DATA COLLECTED

The decision for treatment with Aubagio® must be made prior to and independently from the proposal to enrol the patient into this study

Version number: Final 2.0

and in line with the approved SmPC.

Administration of Aubagio® and monitoring of patients according to the SmPC and safety reporting will be the sole responsibility of the treating neurologist.

Visit 1 (Baseline)

- Eligibility (according to the approved SmPC)
- Informed consent
- Patient demographics (gender, year of birth, smoking history)
- MS disease history (including date of first symptoms, date of diagnosis, number of relapses in the 2 years prior to enrolment, time since last relapse, disability progression (current Expanded Disability Status Scale [EDSS])
- If applicable, previous DMTs, current DMT, treatment start and stop dates, reason for starting/changing treatment
- Prior and concomitant medications
- Medical/surgical history and co-morbidities
- MSIS-29
- MFIS-5
- HADS
- SDMT
- MSISO-19
- TSQM v1.4
- PDDS
- Number of scheduled and unscheduled HCP encounters in the past 12 months.
- Number of emergency visits, if any in the past 12 months
- HRPQ-MS

Safety (AEs/SAEs/AESIs) since first dose of Aubagio will be retrospectively collected upon signature of the Informed Consent Form.

Visit 2 (Month 3) – only performed if part of routine clinical care.

- Prior and concomitant medications
- Number of relapses since last visit
- Treatment adherence number of missed doses since last visit
- Number of scheduled and unscheduled HCP encounters since last visit
- Number of emergency visits since last visit
- Safety information (AEs/AESIs/SAEs).

V3, V4, V5* V6/EOS

- Prior and concomitant medications
- Number of relapses since last visit
- MSIS-29
- MFIS-5
- HADS
- SDMT

- MSISO-19
- TSQM v1.4
- PDDS
- Treatment adherence Number of missed doses since last visit
- Number of scheduled and unscheduled HCP encounters since last visit
- Number of emergency visits since last visit
- HRPQ-MS (months 12 and 24/EOS only)
- Safety information (AEs/AESIs/SAEs)
- * Visit 5 only performed if part of routine clinical practice

Safety

- AEs/AESIs/SAEs since first dose of Aubagio® will be retrospectively collected upon signing Informed Consent Form.
- AEs/AESIs/SAEs will be recorded at each visit according to standard clinical practice
- Up to 3 Monthly telephone calls may be performed as and when needed in order to follow up on potential AEs/AESIs/SAEs.
- Patients will be followed with laboratory monitoring in a regular healthcare setting in line with local approved label requirements and the RMP for Aubagio[®].

STATISTICAL METHODOLOGY

The following represents an overview of planned analyses. Further elaboration of statistical issues will be specified in the Statistical Analysis Plan (SAP).

Sample size determination

The sample size has been calculated in order to assess the primary objective, describe changes in MSIS-29 scores from baseline to month 24. Mean MSIS-29 score on baseline, 24 months and changes during the follow-up (baseline to 24 months) will be calculated with the 95% confidence interval (CI). Taking into account a standard deviation of 20 points in MSIS-29 (Glenn, 2016), a sample size of 100 allows to estimate the MSIS-29 scores with a precision (distance from the mean to the limits of the 95% CI) of about 4 points with a significance level of 0.05. The sample size of 100 patients has been also determined based on the average number of patients at each site within the recruitment period of 2 years.

Analysis populations

The analysis population will include all enrolled patients who received at least one dose of study medication. All study analysis, including safety analysis, will be performed in this population.

Statistical analysis

All recorded clinical observations will be analysed using descriptive statistics.

Primary analysis:

The primary endpoint of change from baseline to month 24 in the MSIS-

29 will be analysed descriptively providing the mean change with 95% CI and also using an analysis of covariance (ANCOVA), adjusting for baseline covariates, including the baseline MSIS-29 value. A p-value below 0.05 will be considered statistically significant.

Additional exploratory pre-specified analysis of the primary endpoint will be performed in at least 4 specific subgroups: treatment naïve patients, patients previously treated with a MS DMT within the past 2 years, injectable switch patients and oral switch patients.

Secondary analyses:

The changes from baseline to month 24, and to each follow-up visit before 24 months visit, in TSQM v1.4, PDDS, MFIS-5, HRPQ-MS v2, MSISQ-19, SDMT and HADS will be tested using the t-distribution. The mean changes between study visits with the corresponding 95% (CI) will be given. If required, an ANCOVA, adjusting for baseline covariates will be performed. A p-value below 0.05 will be considered statistically significant. The evolution of PRO scores during the follow-up period will be also represented graphically.

In addition to PRO scores, the same statistical methods will be used to analyse number of missed doses of Aubagio® (adherence), number of relapses, number of HCP encounters and number of emergency room visits.

Additional exploratory pre-specified analysis of the secondary endpoints will be performed in at least 4 specific subgroups: treatment naïve patients, patients previously treated with a MS DMT within the past 2 years, injectable switch patients and oral switch patients.

Safety analysis

All patients will be evaluated for safety based on incidence, duration, intensity, and seriousness of AEs, SAEs, and AESIs.

Interim Analysis

Final study analysis will be performed after all patients have completed the core study (24 months±1 month), or discontinuation of the study before the 24 months duration. One interim analysis is planned to be performed at 18 months post first patient in. The results of the interim analysis will be used in publications at medical congresses and presentations, providing an update on the study.

ESTIMATED DURATION OF THE STUDY

[figure not shown]
Estimated enrolment duration: 12 months with competitive enrolment.

Estimated date for First Patient In (FPI): Q2 2018

Estimated study duration per patient: 2 years (24 months).

2 FLOW CHARTS

2.1 GRAPHICAL DESIGN OF EVENTS LEADING TO, AND PARTICIPATION IN, THE STUDY

- * Before the consideration to enrol the patient to the study
- a Baseline visit completed within 4 weeks of first dose of Aubagio®
- b Patient-reported outcomes completed within 4 weeks of first dose of Aubagio®

AE = adverse event, SAE= Serious Adverse Event or AESI= Adverse Event of Special Interest; m = months; SmPC = Summary of Product Characteristics

2.2 STUDY FLOW CHART

				Core Study		
Visits (V)	V1	V2 (if part of clinical practice)	V3	V4	V5 (if part of clinical practice)	V6/EOS
Months	Baseline ^a	M3 ±1 month	M6 ±1 month	M12 ±1 month	M18 ±1 month	M24 ±1 month
Eligibility (according to SmPC)	Х					
Patient Information / Informed Consent	Х					
Demographics (gender, year of birth, smoking history ^b)	Х					
MS disease history (date of first symptoms, date of diagnosis, number of relapses in the past 2 years, time since last relapse, disability progression / current EDSS)	Х					
Previous DMTs (previous drugs), current drug, time since treatment) $^{\it c}$	Х					
Reason to start/change DMT	Х					
Prior and concomitant medications	Х	Х	Х	Х	Х	Х
Number of relapses since last visit		Х	Х	Х	Х	Х
MSIS-29	Χď		Xi	X ⁱ	Xi	X ⁱ
MFIS-5	χď		X ⁱ	X ⁱ	Xi	X ⁱ
HADS	χď		Xi	Xi	Xi	X ⁱ
SDMT	Χď		Х	Х	Х	Х
MSISQ-19	χď		Xi	X ⁱ	Xi	Xi
TSQM v1.4	Xc,d		X ⁱ	X ⁱ	Xi	X ⁱ
PDDS	X _q		X ⁱ	X ⁱ	Xi	X ⁱ
Treatment adherence to Aubagio (number of missed doses since last visit)		Х	Х	Х	Х	Х
Number of unscheduled and scheduled HCP encounters ^f	Х	Х	Х	Х	Х	Х
Number of emergency visits ^f	Х	Х	Х	Х	Х	Х
HRPQ-MS	X ^d			X ⁱ		Xi
AEs, AESIs, SAEs ^e	Х	Х	Х	Х	Х	Х

- a Baseline visit completed within 4 weeks of first dose of Aubagio[®].
- b Smoking history includes current/former smoker, average consumption, pack years exposure, and time since cessation of smoking (if applicable).
- *c* Patients with previous DMT.
- d Within 4 weeks of first dose of Aubagio[®].
- e AEs (including SAEs & AESIs) within 4 weeks after first dose of Aubagio® will be retrospectively collected upon signing of the informed consent and on an ongoing basis including scheduled visits (eg., patients should report all AEs, SAEs and AESIs during the study period).
- f For baseline this is over the past 12 months
- g Performed in accordance with the local approved SmPC and the Aubagio $^{\circledR}$ RMP
- h In addition to study visits there may be up to 3 monthly telephone calls in order to follow up on potential AEs/AESis/SAEs
- i As per patient convenience, questionnaires can be completed within one week prior to the visit. Each questionnaire can be completed on a different day. However, a patient must complete an individual questionnaire once it has been started. Note: if a designated caregiver is available to assist the patient, they may physically complete the questionnaire for the patient. A nurse or other health care professional may assist with instructing the patient on how to complete a questionnaire.

AE = adverse event; AESI = adverse event of special interest; DMT = disease-modifying therapy; EDSS = Expanded Disability Status Scale; EOS = end of study; MFIS-5 = Modified Fatigue Impact Scale; HCP = health care professional; HRPQ: Health related productivity questionnaire HRPQ-MS = Health Related

28032018

Version number: Final 2.0

Product observational study protocol TERIFL08182

28032018

Version number: Final 2.0

Productivity Questionnaire V2 (MS); MS = multiple sclerosis; MSIS-29 = Multiple Sclerosis Impact Scale; PDDS = Patient Determined Disease Steps; SAE = serious adverse event; TSQM v1.4 = Treatment Satisfaction Questionnaire for Medications; MSIS-19 = MS Intimacy & Sexuality Questionnaire

4 LIST OF ABBREVIATIONS

AE: Adverse Event

AEP: Accelerated Elimination Procedure
AESI: Adverse Event of Special Interest

DBP: Diastolic Blood Pressure

DMT: Disease Modifying Therapy
eCRF: Electronic Case Report Form
EDC: Electronic Data Capture

EDSS: Expanded Disability Status Scale
EMA: European Medicines Agency
FDA: Food and Drug Administration
HADS Hospital Anxiety and Depression Scale

HCP: Healthcare Provider

HRPQ-MS v2: Health Related Productivity Questionnaire Forms Version 2

HRQL Health Related Quality of Life ILD: Interstitial Lung Disease

IRB/IEC Institutional Review Board/Independent Ethics Committee

MFIS-5 Modified Fatigue Impact Scale – 5 MRI: Magnetic Resonance Imaging

MS: Multiple Sclerosis

MSIS-19 Multiple Sclerosis Intimacy & Sexuality Questionnaire – 19

MSIS-29: Multiple Sclerosis Impact Scale
PDDS: Patient Determined Disease Steps

PRO: Patient Reported Outcome RMP: Risk Management Plan

RRMS: Relapsing Remitting Multiple Sclerosis

SAE: Serious Adverse Event SAP: Statistical Analysis Plan SBP: Systolic Blood Pressure

SGPT Serum Glutamate-Pyruvate Transferase

SDMT Symbol Digit Modalities Test

SmPC: Summary of Product Characteristics

TSQM v1.4: Treatment Satisfaction Questionnaire for Medication Version 1.4

ULN: Upper Limit of Normal

5 INTRODUCTION AND RATIONALE

5.1 BACKGROUND

Multiple Sclerosis (MS) is a demyelinating disease of the central nervous system that affects as many as 2.3 million people worldwide [1]. Its clinical course is typically characterized by initial episodes of transient neurological compromise (relapses) with a recovery period, followed by a phase of cumulative deficits that may increase with each new episode. This is known as Relapsing Remitting Multiple Sclerosis (RRMS). Although patients typically experience some degree of recovery in RRMS, even a single relapse can lead to permanent disability in a substantial number of patients, with a sizeable majority being left with disability after 2 events.

RRMS is a chronic disease that affects people differently, and symptoms which may be physical or non-physical, can range from mild to severe, and may be present, absent or may progress with time [2]. As a neuropsychiatric disease, MS threatens personal autonomy, independence, dignity, and future plans [3].

There is now increasing recognition that there are psychological, social, and psychiatric issues resulting from vital segments of health-related quality of life (HRQoL), which are distinct from disease-related physical disabilities [4-6]. The main neuropsychiatric features include anxiety, depression, cognitive impairment, irritability, and anger [7].

HRQoL measurements are being considered increasingly important with regard to evaluating treatments, anticipating disease progression, and providing comprehensive care to MS patients [4, 5]. Health authorities (FDA and EMA) encourage the use of HRQoL assessments in patients with chronic illnesses [8, 9], and several groups have published detailed recommendations for HRQoL assessments [10, 11].

Despite the acknowledged need to consider HRQoL issues, HRQoL assessment remains under-utilized in routine clinical practice [12]. Recognising this gap and considering the main neuropsychiatric features of MS, the objective of this observational study will be to assess patient reported outcomes (PROs) in patients with RRMS who have initiated treatment with Aubagio® according to the approved Summary of Product Characteristics (SmPC).

5.2 RATIONALE

Aubagio® (teriflunomide; A771726, ATC code L04AA31) is a once-daily, oral disease-modifying therapy (DMT) indicated for the treatment of patients with relapsing remitting MS (RRMS). Aubagio® has shown significant efficacy across a number of key measures for MS disease, including relapse rate reduction, slowing the progression of physical disability and reducing the number of brain lesions as detected by magnetic resonance imaging (MRI) [13-15]. The cumulative exposure to Aubagio® in the clinical program exceeds 6800 patient-years, and in long-term studies individual exposure exceeds 12 years [16]. Aubagio® once-daily 14 mg oral tablets were approved in June 2014 for the treatment of adult patients with RRMS to reduce the frequency of clinical relapses and to delay the progression of physical disability.

The functional consequences of MS disease progression, such as increased fatigue, changes in cognition, increased disability and reduced ability to work are important from the patients' perspective as well as the clinician's and impact overall quality of life [17-20].

Over the past several years, the development of evaluations for PROs has provided the tools to assess patient outcomes in clinical practice and real world settings. Various instruments to collect patient reported outcomes have been developed and validated in MS and provide a means by which patients can document important information on their disease state and the impact of MS treatment on their overall quality of life.

Health authorities (e.g. EMA) encourage the use of quality of life assessment in patients with chronic illness [9], and several groups have published detailed recommendations for HRQoL assessments in the evaluation and approval for medicinal products [10, 11].

Property of the Sanofi group - strictly confidential

TERIFL08182 - teriflunomide

Version number: Final 2.0

Despite the acknowledged need to consider HRQoL, in routine clinical practice these assessments remain underutilized [12]. Recognising this gap and considering the main neuropsychiatric features of MS, the objective of this observational study is to provide real world patient reported outcomes in MS patients treated with Aubagio®. This study will assess PROs measuring HRQoL, treatment adherence and satisfaction, and health economics outcomes in real-life medical practice in patients with RRMS.

Safety will also be assessed by collecting adverse events (AEs), adverse events of special interest (AESIs), and serious AEs (SAEs).

6 STUDY OBJECTIVES

6.1 PRIMARY

The primary objective of this study is to describe the change in HRQoL at 2 years in patients commencing treatment with Aubagio® in routine clinical practice for RMMS.

6.2 SECONDARY

To describe the change in the following PROs at 2 years, in patients commencing on treatment with Aubagio® in routine clinical practice for RRMS:

- Fatique
- Anxiety and depression
- Cognition
- Sexual dysfunction
- Disease progression
- Treatment satisfaction
- Treatment adherence

To describe the number of relapses during the two year study period in patients commencing on treatment with Aubagio® in routine clinical practice for RRMS

To describe health economic outcomes in patients with RRMS treated with Aubagio® assessed by the number of scheduled and unscheduled healthcare provider (HCP) encounters and emergency visits as well as productivity loss.

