7.3.1 Baseline Visit

The following patient characteristics will be recorded at the baseline visit (completed within 4 weeks of first dose of Aubagio®):

- Patient demographics (gender, year of birth, smoking history)
- MS disease history
 - Date of first symptoms: month and year
 - Date of diagnosis: month and year
 - Number of relapses in the 2 years prior to enrolment
 - Time since last relapse
 - Disability progression/Expanded Disability Status Scale (EDSS) score
- Previous/current treatment with DMTs, if applicable
 - Treatment start and stop dates
 - Reason for starting/changing treatment
- Prior and concomitant medications
- Medical/surgical history and co-morbidities
- PROs (collected within 4 weeks of first dose of Aubagio®):
 - Multiple Sclerosis Impact Scale (MSIS-29) questionnaire
 - Modified Fatique Impact Scale (MFIS-5) questionnaire
 - Hospital Anxiety and Depression (HADS) guestionnaire
 - Symbol Digit Modalities Test
 - Multiple Sclerosis Intimacy and Sexuality (MSISQ-19) Questionnaire
 - Treatment Satisfaction Questionnaire for Medication version 1.4 (TSQM v1.4) questionnaire
 - Patient Determined Disease Steps (PDDS) questionnaire
- Number of scheduled and unscheduled HCP encounters within the past 12 months
- Number of emergency visits in past 12 months
- Health Related Productivity Question-MS (HRPQ-MS) questionnaire
- AEs/SAEs/AESIs since first dose of Aubagio® will be retrospectively collected upon signature of Informed Consent Form

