7.3.3 Visits 3, 4, 5 and 6/EOS

The following data will be recorded after initiation of Aubagio® (V3, V4, V5, V6/EOS). Visit 5 will only occur if part of routine clinical practice:

- Prior and concomitant medications
- Number of relapses since last visit
- PROs:
 - MSIS-29 questionnaire
 - MFIS-5 questionnaire
 - HADS questionnaire
 - SDMT
 - MSISQ-19 questionnaire
 - TSQM v1.4 questionnaire
 - PDDS questionnaire
- Treatment adherence number of missed doses since last visit
- Number of unscheduled and scheduled HCP encounters since last visit
- Number of emergency visits since last visit
- Safety information (AEs/AESIs/SAEs)

In addition to the study visits there may be up to 3 monthly telephone calls between the study visits from the sites to the patients as and when needed in order to follow up on potential AEs/AESIs/SAEs. The results of these calls will also be documented in the study CRF.

Patients will be followed with laboratory monitoring in a regular healthcare setting in line with local approved label requirements and the Risk Management Plan (RMP) for Aubagio[®].

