7.4.2 Secondary Endpoints

The secondary variables are clinical outcomes, PROs, and health economics outcomes.

Clinical Outcomes:

Number of relapses (at baseline), at each visit and at month 24

Patient reported outcomes:

• Fatigue: change in Fatigue score, assessed using the MFIS-5, at each visit (except visit 2) and at month 24 (MFIS-5) compared with baseline

- Anxiety/Depression: Change in anxiety/depression at each visit (except visit 2) and at month 24 compared with baseline, as measured by the HADS
- Cognition: Change in cognition at each visit and at month 24 compared with baseline, as measured by the SDMT.
- Sexual Function: Change in intimacy and sexual health at each visit and at month 24 compared with baseline as measured by MSISQ-19
 - Treatment satisfaction: change in TSQM v1.4 score over time, from baseline to each visit (except visit 2) and month 24.
- In patients switching from another DMT: change in TSQM from baseline to month 6 and to month 24
- For naïve patients: change in TSQM from month 6 to month 24
- Disability accumulation: change in PDDS over time at each visit (except visit 2) and at month 24 compared with baseline
- Treatment adherence: number of missed doses of Aubagio®

Health economics outcomes:

- Number of scheduled and unscheduled HCP encounters
- Number of emergency visits
- Change in work capacity reported using the HRPQ-MS at months 12 and 24 compared with baseline.

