8.5 WITHDRAWALS AND DROPOUTS

Patients may withdraw from treatment with Aubagio ® if they decide to do so, at any time and irrespective of the reason, or this may be the Investigator's decision. All efforts should be made to document the reasons for treatment discontinuation, and this should be documented in the eCRF.

If a patient discontinues Aubagio® treatment before month 24, the V6 (month 24/EOS visit) evaluations should be performed as soon as possible.

Patients who have withdrawn from the study cannot be re-included (treated) in the study. Their inclusion numbers must not be reused.

Version number: Final 2.0

Patients who prematurely discontinue participation in the study will not be replaced. The Investigator may continue to enrol patients in the study for the duration of the recruitment phase.

The Statistical Analysis Plan (SAP) will specify how patients who are lost to follow-up for their primary endpoints will be considered.

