14.3.1.2 Secondary Analysis

The changes from baseline to month 24, and to each follow-up visit before 24 months visit, in TSQM v1.4, PDDS, MFIS-5, HRPQ-MS v2, MSISQ-19, SDMT and HADS will be tested using the t-distribution. The mean changes between study visits with the corresponding 95% confidence interval will be given. If required, an ANCOVA, adjusting for baseline covariates will be performed. A p-value below 0.05 will be considered statistically significant. The evolution of PRO scores during the follow-up period will be also represented graphically.

In addition to PRO scores, the same statistical methods will be used to analyse number of missed doses of Aubagio® (adherence), number of relapses, number of HCP encounters and number of emergency room visits.

Additional exploratory pre-specified analysis of the secondary endpoints will be performed in at least 4 specific subgroups: treatment naïve patients, patients previously treated with a MS DMT within the past 2 years, injectable switch patients and oral switch patients.

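### Relapses, HCP encounters and emergency visits are to be analysed as raw counts by t-based methods with no person-time, although V6/EOS is brought forward for early stoppers; if those counts are pooled with full 24-month counts, the two-year mean number of relapses is biased downward.

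*Protocol*

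**What the plan says.** **Objective and endpoints.** Section 6.2 sets the aim as "To describe the number of relapses during the two year study period in patients commencing on treatment with Aubagio® in routine clinical practice for RRMS". The Synopsis gives the endpoint as "Number of relapses (since baseline) at each visit and at month 24"; Section 7.4.2 words it slightly differently but also as a count. The health economics endpoints in 7.4.2 are "Number of scheduled and unscheduled HCP encounters" and "Number of emergency visits". Neither 6.2 nor 7.4.2 attaches a two-year period to these two.

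**Recording.** Sections 7.3.2 and 7.3.3 collect each count at study visits for the interval since the previous one (for relapses, "Number of relapses since last visit"). Counting therefore ends at the last visit made.

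**Early stopping.** Section 8.5 says: "If a patient discontinues Aubagio® treatment before month 24, the V6 (month 24/EOS visit) evaluations should be performed as soon as possible". Section 11.1 has the same rule for premature end of study participation. No later study visit is scheduled. Section 11.4 asks for re-contact about health and vital status after withdrawal, but not for relapse counts.

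**Analysis.** Section 14.2 defines one analysis population, all enrolled patients with at least one dose, and 8.5 says that dropouts are not replaced. Section 14.3.1.2 prescribes the t-distribution, mean changes with 95% CI and, if required, ANCOVA for the questionnaire scores. It then says that "the same statistical methods will be used to analyse number of missed doses of Aubagio® (adherence), number of relapses, number of HCP encounters" and emergency room visits. No rate, person-time or offset appears anywhere in the protocol.

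**The concern.** A questionnaire score taken at an early V6 is a complete score, only taken early. A count taken at an early V6 covers less time and can only be equal to or smaller than the count the same patient would have had at month 24. Using the same method for both overlooks this difference.

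Relapse is the only item listed under clinical outcomes. If early V6 counts are averaged with full counts, the reported figure mixes how often patients relapse with how long they stay on treatment: the more patients stop, the better it looks. The exploratory subgroups (treatment-naïve, previously treated, injectable switch, oral switch) inherit the problem, because different stopping rates would show up as different relapse counts. HCP encounters and emergency visits also mix unequal follow-up.

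**Working it through.** **Figures in the protocol.** It states no expected number of relapses, encounters or emergency visits, and no discontinuation share. Its only computed figure is the MSIS-29 precision in 14.1: 1.96 × 20 / √100 = 3.92 points, against the stated value of about 4. That reproduces and does not bear on this point.

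**Direction.** Let a patient's last count be taken at month T ≤ 24. The count to T cannot exceed the count to 24. Averaged over all treated patients, the expected count is below the true two-year mean as soon as some T < 24 and the event rate after T is above zero. This needs no outside figure, only that early V6 counts enter the average.

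**Size.** Assume a constant event rate. With f the share stopping early and t their mean month of stopping:

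- raw mean / true two-year mean = (1 − f) + f × t/24
- shortfall = f × (1 − t/24)

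Both f and t are assumptions:

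| f | t = 6 | t = 12 | t = 18 |
|---|---|---|---|
| 10% | 7.5% | 5.0% | 2.5% |
| 20% | 15.0% | 10.0% | 5.0% |
| 30% | 22.5% | 15.0% | 7.5% |
| 40% | 30.0% | 20.0% | 10.0% |

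**Example, stopping unrelated to relapse.** Assume 0.3 relapses per year, f = 30%, t = 12.

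- True two-year mean: 2 × 0.3 = 0.60.
- Raw mean: 0.7 × 0.60 + 0.3 × 0.30 = 0.51, which is 15% low.
- Mean observed time: 0.7 × 2 + 0.3 × 1 = 1.7 years. Rate: 0.51 / 1.7 = 0.30 per year, which is correct.

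**Example, early stoppers relapse at twice the rate.** Same f and t, with 0.6 per year in stoppers.

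- True mean: 0.7 × 0.60 + 0.3 × 1.20 = 0.78.
- Raw mean: 0.7 × 0.60 + 0.3 × 0.60 = 0.60, which is 23% low.
- Completers only: 0.60, also 23% low.
- Twice the person-time rate: 2 × 0.60 / 1.7 = 0.71, which is 9% low.

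**Relapse-triggered stopping.** A simulation of 400,000 patients assumed 0.3 relapses per year, 30% of relapses leading to stopping plus background stopping (33% stop overall), and gamma frailty with variance 1. Against a true mean of 0.60, the raw mean was 0.45, completers only 0.36, and twice the person-time rate 0.55. With frailty variance 0.5 the three were 0.47, 0.39 and 0.58. Restricting to completers can therefore be worse than the raw mean. Person-time removes most of the bias but not all of it.

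**The case against.** - **The protocol never says that unobserved time counts as event-free.** This stands. A reader might infer such a rule from the month 24 label on the early visit, but 8.5 and 11.1 govern data collection only. Section 14.3.1 summarises non-missing values, so an early count could be set to missing at month 24. The problem is then selection of completers, not truncation. The finding has to be conditional, but neither route gives a sound two-year number.
- **This is a matter for the SAP.** In part. Section 14.3 says that it gives specifications for the SAP and that differences will be documented there, so the SAP could add a rate. But 14.3.1.2 names a method for these counts, and that method has no place for follow-up time. The only incomplete-follow-up rule that 8.5 expressly leaves to the SAP concerns the primary endpoint. What is criticised is a stated choice.
- **The size is assumed, and sampling error is large.** Correct. With 100 patients and an assumed mean of 0.60, the Poisson 95% half-width is 1.96 × √(0.60/100) = 0.15, or 25% of the mean, and a bias of 10–20% lies inside that. This limits the consequence for a descriptive, single-arm secondary endpoint. It does not excuse a bias of known direction, which the interval does not reflect.
- **A rate changes the quantity, and doubling it extrapolates.** This stands. The rate describes observed follow-up, which is mainly time on Aubagio, and remains biased when relapse drives stopping.

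**Conclusion.** The concern holds in conditional form. If early V6 counts are averaged with full 24-month counts in the single analysis population, the mean number of relapses over two years is biased downward whenever anyone stops early and the later relapse rate is above zero. If they are treated as missing at month 24, the figure describes completers. Under a constant rate the shortfall in the first case is 2.5% to 30% for assumed f = 10–40% and t = 6–18 months.

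Three stronger readings are not supported:

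- A reader might conclude that the two-year figure is certainly understated. The protocol does not fix how an early V6 count enters the month 24 summary.
- A reader might conclude that a two-year total of HCP encounters and emergency visits is understated too. The protocol ties no two-year period to them; what can be said is that their counts mix unequal follow-up.
- A reader might conclude that the bias is small only when few patients stop. Late stopping also keeps it small: f = 30% with t = 18 gives 7.5%.

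The comparison of follow-up counts with the 12-month baseline window for encounters and emergency visits is a separate matter and is not part of this conclusion.

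**What to change.** In 7.4.2 and 14.3.1.2, for relapses, HCP encounters and emergency visits:

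- Report events per observed person-year, counting time from V1 to V6/EOS or last contact.
- Take the 95% CI from a Poisson or negative binomial model with log(observed time) as offset, in place of the t-based interval.
- Show total observed person-years and the number of patients followed to month 24 beside each raw count, overall and by subgroup.
- Describe the rate as applying to observed follow-up. Label any two-year number derived from it as an extrapolation that assumes a constant rate and does not fully correct for relapse-driven stopping.

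The cost is statistical wording only: visit dates and counts are already collected, and no visit or clinical procedure changes. The downsides are a less favourable relapse figure and reliance on a constant-rate assumption.
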